6.4 Interventions

Mindful Living Condition. This is a behavioral web-conferenced group intervention teaching stress reduction, cognitive behavioral therapy (CBT), mindfulness strategies, acceptance and commitment strategies, communication, and other skills during an introductory session and 10 1.5-2 hour sessions facilitated by a clinical psychologist and a graduate student or postdoc.

Table 4.	Weekly	Mindful	Living S	ession	Topics	and	Relaxat	ion/Me	ditation	Exercise	es
----------	--------	---------	----------	--------	--------	-----	---------	--------	----------	----------	----

Wk	Session Topic	Exercises	Linkage to sample OC issues/ concerns
1	Stress response and stress management. Developing an awareness of personal stressors. Finding meaning and sources of personal strength	Progressive muscle relaxation (PMR) & breathing	High levels of stress, and uncertainty Disease/treatment related concerns (e.g., progression, symptom burden)
2	Cognitive Appraisal: Relationships between thoughts, emotions, and physical responses.	Passive PMR with guided imagery	Fear of recurrence/death, bodily changes, dreading the worst with any new symptoms
3	Cognitive Restructuring: Demonstration & discussion on alternative responses to negative self-talk.	Autogenic relaxation	Fear of recurrence, self-image; adjusting expectations; dealing with symptoms
4	ACT: Identification of avoidance and control strategies; finding effective alternatives through personal values, acceptance, and gratitude; using defusion to reduce emotional reactivity; overcoming avoidance	Introduction to Mindfulness, Guided mindful body scan	Fear of recurrence, living in the face of uncertainty in the future, abilities, work, meaning, creating a new normal, avoiding pain and anxiety
5	Coping strategies: problem-focused or emotion- focused coping strategies. Acceptance-based strategies for painful emotions; decreasing avoidance.	Mindfulness meditation	Coping with symptoms, coping with loss of abilities, work challenges, challenges of asking for help, self-nurturance
6	Social support: Benefits & types of support. Strategies for enhancing support and meaningful relationships.	Mindfulness meditation	Changes in relationships, loss of intimacy, avoiding conversations about symptoms, death,

7	Effective communication: Becoming aware of needs and communicating them effectively.	Mindfulness meditation	Expressing needs adaptively & asking for help; doctor-patient and intimate relationships
8	Anger management: Identifying patterns of anger expression and dealing with anger.	Loving kindness meditation	Interpersonal conflict, frustration with health care, assertiveness
9	ACT: Meaning and values: Discussion of personal values, spirituality, meaning in life with respect to cancer. Strategies to deepen meaning and enhance committed action.	Guided relaxation and visualization	Creating a meaningful life in the face of uncertainty, acceptance of a new normal
10	Wrap up: Review & assessing personal growth. Developing a maintenance plan with strategies for living more fully.	Guided relaxation and visualization	Generalizing skills to daily life, redefining roles, empowerment

Health Promotion (HL) Condition (Healthy Lifestyles). This is a web-conferenced group intervention designed to provide relevant lifestyle information for ovarian cancer survivors. The HL arm will provide sessions on ovarian cancer survivorship and quality of life, exercise, nutrition, sleep, stress, cognition, body image, integrative medicine, and development of a lifestyle survivorship plan. There will be a group introductory session and 10 1.5-2 hour sessions facilitated by a health educator and a graduate student or postdoc.

 Table 5. Weekly Health Promotion Session Topics

Week	Session Topic	Linkage to sample OC concerns
1	Common Survivorship Issues	Understanding OC, importance of HRQOL
2	New Directions in Ovarian Cancer Treatment	Understanding new treatment options
3	Exercise and Cancer Survivorship	Benefits/ challenges of remaining active
4	Nutrition and Cancer Survivorship	Appetite changes, adequate nutrition in cancer care
5	Sleep	Healthy sleep maintenance; improving sleep
6	Stress and Health	Importance of stress and stress reduction
7	Cognition, Aging, and Chemo-Brain	Cognitive symptoms & memory challenges
8	Body Image and Sexuality	intimacy and relationships; role changes
9	Integrative Medicine	Finding reliable information on integrative care
10	Wrap-up: Developing a Survivorship plan	Advance planning; survivorship care

Stopping points

Criteria for suspending or terminating the study would be if during the study there is a perceived danger for subjects due to participation. This is not anticipated. However, if during interim analysis we find that more than 25% of subjects in the Mindful Living arm move from a non-depressed state (CESD < 24) to a depressed state (CESD \geq 24) we would evaluate whether the trial should be stopped..

6.5. Risks

Based on our previous work, this study as described is of minimal risk. Minimal risk is defined as the probability and magnitude of harm or discomfort anticipated in the research not greater than that ordinarily encountered in daily life or during routine physical or psychological exam.

During the psychosocial questionnaire administration, there are minimal potential emotional risks to subjects due to the somewhat personal nature of the questions asked regarding mood and quality of life. Answering the questions may make subjects upset or uncomfortable; subjects will be informed that they can choose not to answer questions they do not wish to answer.

During the group conferencing sessions, sensitive topics may be discussed; subjects are free to participate as much or as little as they feel comfortable.

There is a potential loss of confidentiality from the web conferencing format; all subjects will be instructed in confidentiality practices at the beginning of the groups (see below).

Risks of Immune Response Sub-Study

Slight discomfort or stinging sensation when using the lancet. Small risk of infection and/or bruising.

What Is Done To Minimize The Risks

Because interactions will be in a group setting, in the first session subjects will be instructed about the importance of confidentiality. They will be required to access the web-based intervention in a private location where others could not overhear the group conversation. Additionally, subjects can choose to disclose as much or as little personal information as they feel comfortable with in the group. Confidentiality of subject information will be strictly preserved, and subject names will not be revealed in publications or reports.

Subjects will be informed that they may withdraw from the study at any time, with no penalty, should this occur; conversely, we will attempt to resolve any problems causing these responses, should survivors wish to continue participating. If a participant experiences an adverse or unanticipated event during the study, research staff in contact with that participant will notify the lead investigator at each participating site or at UI if the participant is not being followed at one of the participating clinical sites. Subjects will be asked to report any new health problems that arise in connection with the study to the study coordinator at their site or to the Coordinating and Data Core at the UI if they are not from a participating clinical site. He/she will refer the survivor to their physician for serious health problems. Should a survivor disclose high levels of emotional distress (e.g. levels of depression consistent with a diagnosis of depression [CESD > 24]) during the study period, designated study personnel will contact the participant to offer appropriate resources as determined by the lead investigators. Documentation of appropriate resources offered to the survivor and of the survivor's acceptance or rejection of the resources will be made by the Coordinating and Data Core.

Study data will be collected and managed using REDCap (Research Electronic Data Capture) electronic data capture tools supported by the Biomedical Informatics group in the UI Institute for Clinical and Translational Science. REDCap (www.project-redcap.org) is a secure, web-based application with controlled access designed to support data capture for research studies, providing: 1) an intuitive interface for validated data entry; 2) audit trails for tracking data manipulation and export procedures; 3) automated export procedures for seamless downloads to common statistical packages; and 4) procedures for importing data from external sources. For multi-center studies REDCap uses Data Access Groups (DAGs) to ensure that personnel at each institution are blinded to the data from other institutions Each study team member will be granted access to REDCap through a secure login by the study PI, study manager or their proxy. REDCap supports Two-factor authentication using DUO.

Risks of Immune Marker Sub-Study:

For Risks of Immune Response Sub-Study: The process and products in the kit are used routinely in a wide range of healthcare applications, including measurement of blood glucose (blood sugar) in diabetes. The equipment is sterile and following the instructions provided in the kit (like cleaning the area) will minimize infection risk.

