4.2 Temporary Exclusion Criteria

- 1. Survivors involved in Steps through OC must wait until they have completed that program to participate.
- 2. Survivors currently involved in a study involving another behavioral intervention or an exercise intervention must wait until the prior study is over to participate. (In cases 1 and 2, the temporary exclusion will end once survivors have completed their Steps through OC or behavioral intervention or exercise intervention. Study team will note down the date when Steps through OC or the behavioral intervention will end. At this point, the study team will recontact survivors and consent them to the study if they wish to participate.)
- 3. Survivors who score greater than or equal to 24 on the CESD can be rescreened when their depressive symptoms resolve. (In case 3, temporary exclusion will end when a survivor feels that their depressive symptoms have resolved, at which point they will retake the online screening on their own. If survivor's score on the CES-D of the online screening is less than 24 on rescreening, the study team will approach them to be consented if they wish to participate.)

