4.3 Exclusion Criteria

- 1. Non-epithelial ovarian cancer, ovarian tumors of low malignant potential ("borderline"), cancers originating from other organs. Survivor who have a history of a prior cancer besides their ovarian cancer will be considered eligible as long as they are not in active therapy for said other prior cancer.
- History of prior inpatient psychiatric treatment for severe mental illness (e.g. psychosis) or current psychosis, history of bipolar disorder or schizophrenia in the last 2 years or current bipolar disorder or schizophrenia, current major depression (CESD ≥ 24), dementia, history of substance use disorder in the last 2 years or current substance dependence, or organic mental disorder (e.g., dementia).
- 3. Survivors who are younger than 18 or older than 90 years of age
- 4. Unable to meet study requirements.
- 5. Currently receiving primary chemotherapy.
- 6. History of depression is not excluded as long as the survivor is not currently depressed (see #7).
- 7. Survivors who are currently depressed as indicated by a CES-D Score ≥ 24. (As indicated in 4.2.3 above, they can be rescreened once the depressive symptoms resolve.)

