5.1. Primary Outcomes (Endpoints)

Health Related Quality of Life: The Functional Assessment of Cancer Therapy-Ovarian (FACT-O) includes 4 subscales related to dimensions of HRQOL, including physical, functional, social, and emotional well-being and a 12-item ovarian cancer-specific subscale related to ovarian cancer and treatment-specific HRQOL issues.^{28,29}

Current Stress: The Perceived Stress Scale³⁰ contains 14-items assessing feeling in control vs. overwhelmed with current stressors over the last month. Internal reliability and construct validity are high³¹ and scores have previously been associated with illness markers.^{12,32,33}

Depressive Symptoms: The Center for Epidemiological Studies-Depression Scale (CES-D) is 20item measure rating frequency of depressive symptoms over the past week. Scores of 24 or higher are associated with severe clinical depression.^{34,35} The CES-D and its subscales have been strongly related to physiological variables in previous ovarian cancer research.¹²

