6.2 Screening

Potential subjects will be screened for exclusion criteria. Screening for depression will use the CES-D^{34,35}. The Center for Epidemiological Studies-Depression Scale (CES-D) is 20-item measure rating frequency of depressive symptoms over the past week. Scores of 24 or higher are associated with severe clinical depression and will be excluded.^{34,35} The CES-D and its subscales have been strongly related to physiological variables in previous ovarian cancer research.¹² So that they can receive adequate attention, survivors with scores equal to or above 24 will not be included in groups. Instead, they will be mailed a list of resources that they can use to address their health concerns. If the study team has concerns about a subject's ability to understand English for participation in the intervention, the Wide Range Achievement Test (WRAT)⁵⁶ will be administered. Mental health history and current status and substance use will be abstracted from survivor medical records and will be included in screening questions. This screening will occur at the clinical sites for local survivors, will occur at Fred Hutch/University of Washington Cancer Consortium for survivors recruited from Alaska and Montana, and by Redcap screening interface or by phone at the Coordinating Core for survivors from elsewhere. It should be noted that because of time it may require to fill the various cohorts, time between screening and randomization may vary. It is possible that potential subjects may have recurred or gone on active chemotherapy before the start of the trial. This will be assessed in the initial assessment which is done within 1-2 weeks of the study. In the case of such a change, these individuals will still be allowed to participate in the intervention.

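### Section 6.5 names CES-D > 24 as its example score for contacting an enrolled woman, while every other CES-D rule in the protocol counts exactly 24 as depressed

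*Combined protocol and SAP*

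**What the plan says.** Section 6.5 (What Is Done To Minimize The Risks) provides that when a survivor discloses "high levels of emotional distress (e.g. levels of depression consistent with a diagnosis of depression [CESD > 24]) during the study period", designated personnel contact her and offer resources chosen by the lead investigators. The Coordinating and Data Core then records the offer and her response ("Documentation of appropriate resources offered to the survivor").

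The other CES-D rules read as follows:

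- Section 4.2, item 3: "Survivors who score greater than or equal to 24 on the CESD can be rescreened" once symptoms resolve. She may be approached again only if the new score is below 24.
- Section 4.3, item 2 excludes "current major depression (CESD ≥ 24"), and item 7 excludes "Survivors who are currently depressed as indicated by a CES-D Score ≥ 24".
- Section 5.1: "Scores of 24 or higher are associated with severe clinical depression".
- Section 6.2 (Screening): "survivors with scores equal to or above 24 will not be included in groups". These women are mailed a list of resources instead.
- Section 6.4 (Stopping points): a review of whether to stop is triggered if more than 25% of Mindful Living subjects "move from a non-depressed state (CESD < 24) to a depressed state", the latter being a score of 24 or more.

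**The concern.** Section 6.5 presents its bracketed score as marking depression consistent with a diagnosis. Section 4.3 marks current depression by a different inequality. The two differ at one score, 24.

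This text governs a safety action for an individual participant, and it is the only place where the protocol attaches a number to contacting an enrolled woman. A score that bars entry, and that can count toward a trial-level safety review, should not sit outside the example that staff are given for offering help. Staff work at three clinical sites and a coordinating core, so the one number supplied is a natural one to apply. At stake is whether a woman at 24 is prompted for the contact and the documented offer, or whether that depends on how a staff member reads an example.

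**Working it through.** The plan gives no figure to reproduce here. The check compares the rules and then makes a rough estimate of how often the difference could arise.

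**Step 1. Set the rules side by side, assuming whole-number totals.**

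| Provision | Score 23 | Score 24 | Score 25 |
|---|---|---|---|
| 4.2 item 3 (temporary exclusion) | may be approached | excluded | excluded |
| 4.3 items 2 and 7 | not depressed | depressed | depressed |
| 5.1 (instrument) | below cut-off | severe range | severe range |
| 6.2 Screening | may join | kept out, resources mailed | kept out, resources mailed |
| 6.4 Stopping points | non-depressed | depressed | depressed |
| 6.5 (contact example) | outside example | **outside example** | inside example |

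Only the last row treats 24 like 23. Replacing > with ≥ in that row makes all six provisions agree.

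**Step 2. Is there another numeric trigger for enrolled women?** The mailed list in Section 6.2 goes to women kept out at screening. The 25% rule in Section 6.4 concerns the trial, not an individual. Neither is a contact rule for an enrolled participant, so Section 6.5 stands alone.

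**Step 3. How many women might be at 24?**

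Inputs from the documents:
- 256 women enrolled (Section 4)
- between-subject SD 7.6 and residual SD 5.3 for the CES-D (Table 6)
- 25% dropout (Section 7)
- four scheduled CES-D assessments after enrolment: pre-randomization and weeks 12, 26 and 52 (Table 3)

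Inputs assumed, because the documents do not give them:
- mean CES-D μ from 8 to 16
- score range 0 to 60
- a normal or gamma shape for each woman's underlying level
- in scenario B, a 3-point fall after baseline and steady dropout

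Model: underlying level T has mean μ and SD 7.6. Each observed score is round(T + e), with e ~ N(0, 5.3), held within 0 to 60. Only women with a screening score below 24 are kept. Four later scores are drawn independently given T, and counts are scaled to 256 (1,000,000 simulated women per setting).

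| Scenario | Ever ≥ 24 | Highest score exactly 24 | Readings exactly 24 |
|---|---|---|---|
| A: full completion, no change | 17–73 | 3.2–11.7 | 5.5–23.9 |
| B: retention 100, 91.7, 83.3, 75%; 3-point fall | 10–48 | 2.1–9.0 | 3.2–14.8 |

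Ranges run over the assumed means and both shapes. Taking A and B together, roughly 2 to 12 women peak at exactly 24, that is 2.1/256 = 0.8% to 11.7/256 = 4.6%. If the between-subject SD also varies from 4 to 10, the range widens to 1.3–16.0.

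These are women who score 24. They are not women who go without contact.

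**The case against.** **The score is not the operative test.** The duty attaches to high emotional distress, and the number is a bracketed illustration. Item 7 of Section 4.3 says that a score of 24 indicates current depression, so a woman at 24 arguably meets the verbal description already. This largely stands, and it is why the point is minor. It does not remove the mismatch: the example permits contact at 24 but does not prompt it.

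**Other safeguards exist.** Both arms have live facilitated sessions (Section 6.4), adverse events are reviewed from week 1 to week 52 (Table 3), and participants are asked to report new health problems connected with the study (Section 6.5). This also stands, although none of these is tied to a CES-D score. The surveys are completed from home (Section 8.1), and the three follow-up assessments come after the last weekly session in week 11.

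**The symbol may have been lost in reading the PDF.** This cannot be excluded. Section 7.3 gives the age groups as below and above 65, leaving 65 unassigned, so loose notation is another possible explanation. Against a misreading, the symbol survives in Section 4.3, in the stopping text of Section 6.4 and in Appendix 10.1. The doubt remains, but it is not a refutation.

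**Stronger readings that the documents do not support.**
- A reader might infer that women at 24 are denied help, or that 2 to 12 women would be missed. Nothing in Section 6.5 bars contact at 24, and the count is of scores, not of missed offers.
- A reader might infer that every scheduled CES-D should trigger a contact check. Section 6.5 is written around what a survivor discloses. Turning it into score surveillance is a separate proposal that the mismatch does not require. It would also raise the question of what a pre-randomization score of 24 means for eligibility.
- Because the CES-D is a primary outcome, a reader might infer an effect on the efficacy result. The mixed model in Section 7.1 does not use the contact threshold.

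**Conclusion.** The inconsistency is real in the supplied text. Section 6.5 is the only CES-D provision that leaves 24 off the depressed side, and it holds the only number for contacting an enrolled woman. Severity is minor.

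The estimate of roughly 2 to 12 of 256 women rests on the assumed mean of 8 to 16, the Table 6 SDs and the assumed course over time, and it includes the pre-randomization assessment. The number who would actually miss contact cannot be derived from the documents and could be zero. Sample size, power and the primary analyses are untouched. The conclusion is conditional on the source page printing > and not ≥.

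**What to change.** Check the source page. If it prints >, change CESD > 24 to CESD ≥ 24 in Section 6.5, leaving the rest of the provision, including its status as an example, as it is.

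The edit is one character. Its downside is a small number of extra contacts. If every reading of exactly 24 at the four scheduled assessments led to one, the Step 3 scenarios at Table 6 SDs give about 3 to 24 across the trial. The revised wording does not require that, and some of those women might be contacted anyway.

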6.6. Benefits

There may or may not be benefits to subjects in the study, however, risks are minimal. Subjects have the possibility of learning useful information about stress management, meditation, and

health promotion that may provide benefit to them. The results of the study may support efficacy of an intervention that may improve health related quality of life and decrease distress among ovarian cancer survivors. Moreover, this study will allow ovarian cancer survivors to connect with each other independent of rural/urban residence without the need for travel. Thus, we believe that the risks are reasonable in relation to the anticipated benefits.

6.7. Potential benefits to society in terms of knowledge to be gained

This study addresses an unmet need in ovarian cancer survivors- that is a group psychosocial intervention to address distress and/or to provide information about healthy lifestyle practices that are relevant to ovarian cancer. Our ultimate goal is to substantially improve outcomes in an understudied group of cancer survivors (ovarian cancer) with a high level of mortality by developing actionable strategies to address modifiable psychosocial factors to improve health related quality of life. Thus, this work is of great clinical and public health significance.

7. Statistical Evaluation/Considerations

Descriptive statistics will be computed for all demographic and baseline variables for each of the treatment arms and distributions of continuous variables will be evaluated for normality. If data are non-normal, appropriate transformation will be applied or non-parametric methods may be used. Demographic and baseline variables will be compared between treatment groups using ttest for continuous variables, Wilcoxon-rank sum test for ordinal, and non-normally distributed continuous variables, and Pearson Chi-square test for categorical variables. Variables found to differ significantly between the groups will be used as covariates in the comparison of outcome measures between the treatment groups. A number of variables known to influence our primary outcomes (e.g., income, education, marital status, and race/ethnicity) will be considered as possible covariates. These putative control measures will be analyzed as covariates if they are correlated with our outcomes (at p<.10). The internal consistency (coefficient alpha) and testretest correlations over the course of data collection will be evaluated for multi-item inventories. While every effort will be made to follow-up with subjects, it is expected that approximately 25% of the subjects may be lost across the study period. Intent to Treat (ITT) analysis will be performed using all available data for all randomized subjects. Reasons for subject drop-out will be recorded and compared between treatment groups. Subject characteristics and outcome measures collected prior to drop-out will be compared to those that complete the study follow-up. In the presence of missing data, under the assumption of missing at random (MAR), linear mixed model analysis, which can handle incompletely observed subjects and uses a likelihood estimation method, will provide correct likelihoods and lead to valid estimates. However, since the data under analysis cannot distinguish if data is MAR or if it is missing not at random (MNAR), sensitivity analysis will also be performed using pattern mixture models. Multiple imputation will be used for sensitivity analysis by imputing from a non-random pattern mixture model. Per protocol analyses will be performed including participants that attended at least 6 sessions of their respective intervention condition and completed the immediate post-intervention surveys or any subsequent follow-up surveys.

Aim 1 tests whether the Mindful Living vs. HL intervention increases HRQOL, and decreases in perceived stress (primary), and decreases anxiety, depressive mood, and fatigue (secondary) during a 11-week intervention, and whether changes are sustained over a 12-month follow-up. Based on preliminary data, there will be a detectable differences in mean immediate (post-treatment) change from baseline and in mean sustained change (6 and 12 month) from baseline, for the primary and secondary outcome measures between the ML and the HL arms with an anticipated final sample size of 192 subjects. The detectable group mean difference was calculated for a two-tailed test at the 0.05 significance level with 0.80 power for a final sample

size of 96 subjects per treatment arm for a cluster-randomized design with corresponding intracluster correlation coefficient (ICC) estimated from our pilot data. The 96 subjects are from 16 web-groups (cohorts) per arm with an average of 6 subjects per cohort. This assumes 25% dropout, so that a total of 256 subjects will be enrolled, comprised of 32 cohorts, with 8 subjects per cohort, that will be randomized to one of the two treatment arms. Based on the calculations below we anticipate that our sample size and the variability in our data will enable us to detect smaller intervention effects than those observed in our pilot for our primary variables and for several of our secondary variables for Aims 1 and 2. The effect sizes we anticipate being able to detect are consistent with the medium effect sizes generally observed in other studies of psychosocial interventions in cancer survivors.

	SD		Detectable difference (effect size=diff/pooled SD)			Between Group Difference in Immediate Change (from pilot)	
Outcome Variables Aim 1	Between Subject	Residual	ICC	Immediate (Post-tx)	Sustained (6 and 12 mo.)	Observed Mean (effect size)	95% CI
FACT-Total	13.6	9.3	0.010	5.5 (0.19)	6.1 (0.46)	9.1 (0.69)	(-3.7, 22.0)
PSS	7.1	4.2	0.010	2.5 (0.29)	2.8 (0.47)	-6.7 (-1.13)	(-12.6, - 0.9)
CESD	7.6	5.3	0.150	4.1 (0.34)	4.5 (0.60)	-5.8 (-0.77)	(-13.0, 1.5)
POMS-anxiety	4.1	2.9	0.078	2.0 (0.49)	2.2 (0.54)	-2.0 (-0.49)	(-6.0, 1.9)
POMS-fatigue	4.6	2.9	0.204	2.4 (0.59)	2.7 (0.66)	-2.0 (-0.49)	(-5.9, 1.9)
AIM 2							
MOCS relaxation	1.4	1.2	0.125	0.9 (0.53)	1.0 (0.59)	3.0 (1.77)	(1.0, 5.0)
MOCS coping	4.1	1.8	0.010	1.1 (0.43)	1.2 (0.47)	3.8 (1.49)	(0.7, 6.9)
FMI	7.4	3.5	0.010	2.1 (0.42)	2.3 (0.46)	3.5 (0.71)	(-1.7, 8.8)
AAQ	2.8	2.5	0.284	2.3 (0.65)	2.5 (0.71)	-2.7 (-0.76)	(-6.3, 1.0)

Table 6. Power Considerations

7.1. Statistical analyses for Aim 1

Aim 1 will be tested using linear mixed model (LMM) analyses for repeated measures with treatment group (ML vs. HL), time, and treatment*time interaction as fixed effects. Random effects include web group cohort (within treatment) and subjects (within cohort, within treatment). In fitting the LMM, appropriate covariance structures for the longitudinal measures within subject will be considered, such as compound symmetry, or heterogeneous compound symmetry, and then selected based on Akaike Information Criteria (AIC) and Schwarz's Bayesian Information Criteria (BIC). Specifically, to test for immediate change (post-intervention), the linear mixed model analysis will include the baseline and immediate post-intervention timepoints. The difference in immediate change post-treatment between the different conditions will be tested by the interaction effect. For the mixed model analysis of long-term change, data from all 4 timepoints will be used in fitting the model, with the difference in long-term change at 6 and 12 months assessed using tests of mean contrast. Bonferroni adjustment will be applied to the p-value to test for long-term change at 6 and 12 months. For each of the two analyses, if confounding variables are found to differ between the treatment groups such that covariate adjustment is necessary, a secondary comparison of the primary outcome variable between treatment groups will be made by expanding the LMM to include covariates. These variables may include age, education, income, race/ethnicity, geographic location, recurrence, maintenance chemotherapy, recurrence during the study period, and disease stage. Statistical significance for efficacy of ML vs. HL will be based on a two-tailed test at the 0.05 significance level with treatment effect summarized as mean difference with 95% confidence interval. Similar analyses will be performed for the secondary outcome measures.

7.2. Statistical analyses for Aim 2

The statistical analyses for Aim 2 will examine potential mediators of any observed intervention effects on outcome measures, with examination of skills that support post-intervention and sustained skills. For Hypothesis 2A effects of the intervention on relaxation, coping, mindfulness and acceptance outcomes, the analytic plan will be similar to those in Aim 1, with similar targeted effect sizes and similar power projections. For Hypothesis 2b, testing mediation of intervention effects, mediation analysis will explore the causal pathway between intervention (ML and HL) and changes in primary outcomes (HRQOL, depressed mood, and perceived stress) and secondary outcomes (anxiety and fatigue) from baseline to post-intervention (immediate) and from baseline to 12 months (sustained) with change in reported relaxation, mindfulness, acceptance, and cognitive coping skills as mediators. With the independent variable X (intervention) randomized to web-group cohorts, and the mediator variables M (change in mastery in relaxation, mindfulness, avoidance, and cognitive coping skills), and the dependent variable Y (change in HRQOL, depressive mood, stress, and secondary variables) measured at the subject level within cohorts, we have a two-level hierarchy with a 2-1-1 design. For this multilevel design, multilevel structural equation modeling (MSEM) will be used to estimate and test the direct and indirect effects to assess multilevel mediation⁵⁷ using SEM or GSEM in Stata or MPLUS.

Power for Hypothesis 2B is based on the pilot data where large effects of group assignment (ML vs. HL) were observed on changes in potential mediators (relaxation, coping skills, mindfulness, and acceptance; range of d = .70-1.7). In the proposed model multilevel mediation framework this effect will include some variance attributable to the cohort to which the subject is randomized within the treatment arm, as well as the effect of the treatment itself, the latter of which is the effect of interest. We therefore conservatively estimate the true treatment effect for the mediators to be d = .60, representing the first arm of the mediation pathway. The second arm of the mediation pathway reflects the association between change in the mediators (relaxation, coping, mindfulness, and acceptance) and change in the outcomes of interest (HRQOL, stress, etc.) In our pilot work shown above, the absolute correlation values between these change variables ranged from .41-.76, corresponding to a d range of .89-2.3,58 and we conservatively adopt this lower estimate (.89) for purposes of estimating power. Here we use the Monte Carlo approach for evaluating indirect (mediation) effects with 5000 replications and two Monte Carlo draws per repetition and an attrition-adjusted sample size of 192 (96 per group).⁵⁹ This produces power in excess of .99 for calculating significant mediated effects with a 95% confidence interval. In the event that the true effect sizes are substantially smaller (i.e., d=0.4 rather than .6 for the first path, and d = .6 rather than .89 for the second path) we will still have .80 power to detect significant mediated (indirect) effects.

7.3. Statistical Analyses for Aim 3

Aim 3, an exploratory aim, provides the opportunity to determine whether the effect of the intervention varies as a function of moderators such as rural residence, age, and specific clinical characteristics. For example, it is possible that subjects in rural areas might benefit more from the intervention because they have less access to connections with other survivors and health care information. Survivors who are closer to diagnosis or those who have not recurred may have more interest in acquiring information and skills that will assist them in negotiating their survivorship. Alternatively, survivors who are farther from diagnosis may have had more experience negotiating survivorship issues and may be more open to receiving new skills. Survivors who have recurred may be more highly motivated to develop new skills and acquire new information. As this Aim is

exploratory there are no directional hypotheses. The purpose of this Aim is to provide data for future research with this program to determine whether there are specific individual characteristics that make them more or less likely to benefit from the intervention. As an exploratory aim, Aim 3 is not powered for definitive results but to examine possible trends. To test Hypothesis 3, the LMM analyses described for Aim 1 will be expanded to include one of the factors of interest (rural vs. urban residence, recurrence (0,1), disease severity (early vs. advanced-stage), or time since diagnosis), age (< 65; >65). The model will include the factor as a main effect, and interaction effects with treatment and time (i.e. factor*treatment, factor*time, and factor*treatment*time). If any interaction effect is found to be statistically significant, specific tests of mean contrast will be performed to assess for intervention effect by the factor subgroups, with appropriate Bonferroni adjustment applied to the p-values to account for the number of tests.

